2.5.2 Statistical hypothesis, model, and method of analysis

The co-primary endpoints of this study are PASI 75 response and IGA mod 2011 0 or 1 response at Week 12.

The statistical hypothesis is that secukinumab 300 mg (2 mL AI) is not superior to placebo with respect to the proportion of subjects with PASI 75 response and IGA mod 2011 0 or 1 response at Week 12.

Let p_j denote the proportion of PASI 75 responders at Week 12 for treatment group j and r_j denote the proportion of IGA mod 2011 0 or 1 responders at Week 12 for treatment group j, $j = 1, 0$ where,

- 0 corresponds to placebo
- 1 corresponds to secukinumab 300 mg (2 mL AI)

The following hypothesis will be tested:

- $H_1: p_1 - p_0 \leq 0$ versus $H_{A1}: p_1 - p_0 > 0$,
- $H_2: r_1 - r_0 \leq 0$ versus $H_{A2}: r_1 - r_0 > 0$

In other words:

H_1 : Secukinumab 300 mg (2 mL AI) is not superior to placebo with respect to PASI 75 response at Week 12

H_2 : Secukinumab 300 mg (2 mL AI) is not superior to placebo with respect to IGA mod 2011 0 or 1 response at Week 12

The primary analysis method will be the logistic regression with treatment group (secukinumab 2mL AI vs Placebo); baseline bodyweight strata and baseline PASI score as explanatory variables. Odds ratios will be computed for comparisons of secukinumab dose regimen versus placebo utilizing the logistic regression model fitted. In case of the logistic regression does not converge due to low response rates in the placebo group, an exact logistic regression will be performed and the detailed analysis is described in Section 4.2.3. In case of response rates of 0% or of 100% in one of the treatment groups, confidence intervals and p-values from the t-test for the risk difference comparing to 0 will be provided for the analyses using multiple imputation; for the analyses using non-responder imputation, Fisher's exact test will be performed and confidence intervals for risk difference will be provided.

If logistic regression model does not converge the following steps will be performed:

1. Run the PROC GENMOD procedure with EXACT statement;
2. If convergence not reached, remove the covariates from the model one by one until convergence is reached; start with continuous covariates (baselines PASI score), followed by removing categorical covariates (i.e., weight stratum etc.,);
3. If convergence not reached, perform Fisher's exact test.

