3.1 Primary endpoint (co-primary endpoint)

With respect to the co-primary endpoint (PASI 75 response and IGA mod 2011 0 or 1 response at Week 12), the type-I-error will be 2.5% one-sided for comparison. With 40 subjects per group and assuming a response rate of 8% for PASI 75 response and IGA mod 2011 0 or 1 response in the placebo group, the power to show a response rate of 62% for PASI 75 response and 55% for IGA mod 2011 0 or 1 response in the secukinumab 300 mg (2 mL auto-injector s.c.) group based on Fisher's exact test (nQuery Advisor 7.01, two group Fisher's-exact test of equal proportions) is above 99% for PASI 75 response and IGA mod 2011 0 or 1 response.

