ESTIMATE "OR. AIN 300 mg 2mL PFS VS. Placebo" <treatment> 1 0 -1/exp;  
ESTIMATE "OR. AIN 300 mg 2x1mL PFS VS. Placebo" <treatment> 0 1 -1/exp;  
ODS OUTPUT Estimates=Estimates;  
RUN;
```

The MIANALYZE procedure expects the parameter estimate in the variables ESTIMATE, and the corresponding standard error in the variable STDERR. Measurements can be obtained from “Estimates” dataset by selecting the row with ODDS ratio estimates.

```
Data <modified dataset>;  
set Estimates;  
if substr(label,1,3)= "Exp";  
ESTIMATE=LBetaEstimate;  
STDERR=StdErr;  
effect= "OR";  
if missing(ESTIMATE) or missing(STDERR) then delete;  
RUN;
```

The estimates and standard errors based on the 100 imputed data are then combined by applying Rubin’s rules for multiple imputed data sets, see [Little and Rubin \(2002\)](#).

Programming notes:

- The variables ESTIMATE and STDERR in the input data set for the MIANALYZE procedure may not be missing. Records with missing values need to be deleted and the variable _IMPUTATION_ needs to be renumbered and regenerated since for each by-group the procedure expects consecutive numbers starting at 1.

- The ESTIMATE and STDERR in terms of odds ratios from logistic regressions will be transformed to follow a normal distribution before MIANALYZE procedure. They will be transformed back to Odds Ratio to get the corrected ESTIMATE and corresponding CIs.

The SAS procedure MIANALYZE will be applied as follows:

```
DATA <modified dataset_t>;
  SET <modified dataset>;
  estimate=log(ESTIMATE);
  stderr=(log(LBETAUPPERCL)-log(LBETALOWERCL))/(2*1.96);
RUN ;

ODS LISTING CLOSE;
ODS OUTPUT ParameterEstimates=<results> VarianceInfo=<varinfo> ModelInfo=<modelinfo>;
PROC MIANALYZE PARMs=<modified dataset>;
  BY <by-variables>;
  MODELEFFECTS ESTIMATE;
  SETDERR stderr;
RUN;
ODS LISTING;

data <results_back>;
  set <results>;
  estimate=exp(ESTIMATE);
  LCLMEAN=estimate*exp(-1.96*stderr);
  UCLMEAN=estimate*exp(+1.96*stderr);
RUN ;
```

In case if logistic regression does not converge, risk difference estimates will be provided. The SAS procedure PROC FREQ for risk difference estimates will be applied as follows:

```
ODS LISTING CLOSE;
PROC FREQ DATA=<Imputed dataset> ORDER=DATA;
  TABLES <treatment group>*<response variable>/riskdiff alpha=0.05;
  BY <By-variables>;
  ODS OUTPUT RiskDiffCol1=RiskDiffCol1;
RUN;
ODS LISTING;
DATA DRISK; SET RiskDiffCol1;
  WHERE control= "1" ;
  ESTIMATE=risk;
  STDERR=ase;
  effect="Riskdiff";

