  IF missing(ESTIMATE) OR missing(STDERR) THEN DELETE;
RUN;
PROC SORT DATA=DRISK; BY <By-variables>; RUN;
ODS LISTING CLOSE;
ODS OUTPUT ParameterEstimates=results VarianceInfo=varinfo ModelInfo=Modelinfo;
PROC MIANALYZE PARMs=drisk;
  by <By-variables>;
  modeleffects Riskdiff;
  stderr ase;
RUN;
```

```
ODS LISTING;  
DATA results2;  
  set results;  
  or=estimate*100;  
  lowercl=(LCLmean)*100;  
  uppercl=(UCLmean)*100;  
  KEEP <response variable> <By-variables> or lowercl uppercl probt;  
RUN;
```

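### The SAP's multiple-imputation risk-difference listing does not fix treatment or response order, so in a rare fallback the AI-minus-placebo difference can come out with the wrong sign

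*SAP*

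**What the plan says.** SAP 2.5.2 defines the co-primary hypotheses as AI rate minus placebo rate. When an arm has 0% or 100% response, it states that "confidence intervals and p-values from the t-test for the risk difference comparing to 0 will be provided for the analyses using multiple imputation". SAP 2.6.2 analyses PASI 90 in the same way. SAP 5.4.4 also offers the risk difference when the logistic model does not converge, and gives a listing for it.

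The listing has these steps:

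- It tabulates treatment by response in each BY group, using "PROC FREQ DATA=<Imputed dataset> ORDER=DATA".
- It requests the risk difference without naming a column, and stores only the first column: "ODS OUTPUT RiskDiffCol1=RiskDiffCol1".
- It filters and sorts that output, pools it in MIANALYZE, multiplies by 100, and ends with "KEEP <response variable> <By-variables> or lowercl uppercl probt".

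The only sort shown acts on the output of PROC FREQ, not on its input. The instruction to model the probability of response = 1 belongs to the GENMOD step. SAP 5.4.5.4 defines a risk difference as investigational minus control, so the target is clear, but the listing does not enforce it.

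**The concern.** ORDER=DATA arranges rows and columns by first appearance in the input. The first record therefore sets both orders: its arm becomes row 1 and its response becomes column 1. If that record is an AI non-responder, the stored quantity is AI non-response minus placebo non-response, which is the intended difference with its sign reversed.

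SAP 2.1 bases hypothesis tests on one-sided p-values in favour of secukinumab, so the sign decides the conclusion. The AI-first layout is also plausible, because the GENMOD contrasts in 5.4.4 imply the order AI, PFS, placebo. A confirmatory fallback should not depend on which record happens to come first.

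**Working it through.** **Inputs.** SAP 3.1: "the type-I-error will be 2.5% one-sided for comparison"; "With 40 subjects per group and assuming a response rate of 8"% on placebo; "the power to show a response rate of 62% for PASI 75 response and 55% for IGA mod 2011 0 or 1 response". SAP 3.1.1: 46% for PASI 90. SAP 3: published placebo rates of 3% to 7%. SAP 5.4.4: 100 imputations.

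**The plan's own figure.** SAP 3.1 says power "is above 99% for PASI 75 response and IGA mod 2011 0 or 1 response". Exact one-sided Fisher power with 40 v 40 is 99.97% (62% v 8%) and 99.72% (55% v 8%). PASI 90 (46% v 8%) gives 97.3%, against a stated figure above 90%. The sample size is not in question.

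**Sign of the coded difference.** The code was emulated as row 1 minus row 2 for column 1, both set by the first record. The example has 25/40 AI responders.

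| First record | Placebo 0/40 | Placebo 3/40 |
|---|---|---|
| AI responder | +0.625 | +0.55 |
| AI non-responder | -0.625 | -0.55 |
| Placebo non-responder | +0.625 | +0.55 |
| Placebo responder | not possible | -0.55 |

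With 0/40 on placebo, the SE is sqrt(0.625 x 0.375 / 40) = 0.077 whichever record comes first. The correct result is +0.625 (95% CI 0.475 to 0.775), with one-sided p about 1.6E-16. The reversed result has one-sided p about 1.

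**Chance of reversal, AI first and no pre-sort by response.** This equals 1 minus the AI response rate:

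- PASI 75: 1 - 0.62 = 38%
- IGA 0/1: 1 - 0.55 = 45%
- PASI 90: 1 - 0.46 = 54%

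If placebo is first, reversal needs a placebo responder as first record: 8% at the planned rate, and impossible at 0/40.

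**Chance of the 0/40 placebo trigger.** (1 - p)^40:

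- 0.92^40 = 3.6%
- 0.93^40 = 5.5%
- 0.97^40 = 29.6%

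**Joint chance for PASI 75, AI first.** 0.0356 x 0.38 = 1.4% at an 8% placebo rate, and 0.296 x 0.38 = 11% at 3%.

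**Conditional case: the first AI record is itself imputed.** Assume that ORDER=DATA is resolved separately in each BY group, that 24 of the other 39 AI subjects respond, and that placebo is 0/40. A set gives +25/40 = +0.625 if the first subject is imputed as a responder, and -24/40 = -0.600 otherwise. Rubin's total variance is T = W + (1 + 1/100)B.

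For a 50:50 split:

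- pooled difference = 0.5 x 0.625 - 0.5 x 0.600 = 0.0125
- W = 0.0059
- B = (1.225/2)^2 x 100/99 = 0.379
- T = 0.0059 + 1.01 x 0.379 = 0.389, so SE = 0.62

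| First record imputed as responder | Coded pooled difference (SE) | One-sided p | Fixed-order difference (SE) |
|---|---|---|---|
| 90 of 100 sets | +0.50 (0.38) | 0.094 | +0.62 (0.08) |
| 50 of 100 sets | +0.01 (0.62) | 0.49 | +0.61 (0.08) |
| 0 of 100 sets | -0.60 (0.08) | about 1 | +0.60 (0.08) |

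**The case against.** The listing is a template with placeholders and visible typing slips. The trial has three analysis arms but this code yields one two-arm difference, so some unshown data step must come before it. With the AI first, that step could also sort by descending response, which would remove the problem. This stands as a reason for caution, but the SAP shows no such step and presents the code as what will be applied.

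The direction of the estimand is fixed in 2.5.2 and 5.4.5.4. This is true. What is missing is a code option, not a definition.

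The SAP is not uniform on when this code decides a test. For 0% or 100% response, 2.5.2 gives the t-test under multiple imputation, while 5.4.3 gives Fisher's exact test. For non-convergence, 2.5.2 and 5.4.3 go through exact regression, covariate removal and Fisher's test, while 5.4.4 goes to the risk difference. This also stands, and it narrows the reach of the point.

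A reader might infer that a reversal would go unnoticed, because the retained p-value is two-sided by default and does not change with the sign. The documents do not support that. The same statement keeps the signed estimate and both limits, and response rates by arm are tabulated under multiple imputation (5.4.4) and plotted at Week 12 (5.4.2). A value of -62 points beside rates of 62% and 0% would be conspicuous.

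A reader might also infer that the sign will flip between imputed sets. That needs the first record's Week 12 outcome to be imputed or the record order to vary between sets. It also needs ORDER=DATA to be resolved within each BY group, which was not verified in SAS. The documents give no missing-data rate from which to judge how often this would arise.

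**Conclusion.** The point holds as a minor correction to the code of a fallback analysis. As written, the listing does not guarantee the AI-minus-placebo difference that the SAP defines. With the AI first and no pre-sort by response, the sign is reversed with probability 38%, 45% and 54% for PASI 75, IGA 0/1 and PASI 90, given that the fallback is used. Combined with the 0/40 placebo trigger, the PASI 75 figure is about 1.4% at an 8% placebo rate and up to about 11% at 3%. With placebo first and no placebo responders, the sign is right, because row and column reverse together.

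These figures assume 40 subjects per arm, a record order unrelated to response, independence between arms, and a filter that selects the difference row of the saved table. SAS was not run. Attenuation across imputed sets is a conditional possibility, not an expected result. It would be wrong to conclude that the primary analysis or the power is at risk: the main logistic model fixes response = 1 and is unaffected.

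**What to change.** In SAP 5.4.4:

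1. Restrict the input to the two arms being compared.
2. Replace ORDER=DATA with a fixed order, for example ORDER=INTERNAL, with the AI coded as row 1, placebo as row 2, and response coded 0/1.
3. Request and save the response = 1 column, for example RISKDIFF(COLUMN=2) with RiskDiffCol2, and take its difference row.
4. Before MIANALYZE, check in every imputed set that the saved value equals the AI response rate minus the placebo response rate.

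The cost is a few words of code and one QC line. It needs no new data and changes neither the estimand nor the alpha, and there is no other downside.

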6.3.2 Treatment assignment, randomization

At Randomization visit, all eligible subjects will be randomized via Interactive Response Technology (IRT) to one of the treatment arms. No re-randomization will be done at Week 12 as the original randomization is already including the Period 2 treatment group to be assigned to for Non-responders of the placebo arm. The investigator or his/her delegate will contact the IRT after confirming that the subject fulfills all the inclusion/exclusion criteria. The IRT will assign one randomization number to the subject, which will be used to link the subject to a treatment arm and will specify a unique medication number for the package of study drug to be dispensed to the subject. The randomization number will not be communicated to the subject.

The randomization numbers will be generated using the following procedure to ensure that treatment assignment is unbiased and concealed from subjects and investigator staff. A subject randomization list will be produced by the IRT using a validated system that automates the random assignment of subject numbers to randomization numbers. These randomization numbers are linked to the different treatment arms, which in turn are linked to medication numbers. A separate medication list will be produced by or under the responsibility of Novartis Global Clinical Supplies using a validated system that automates the random assignment of medication numbers to packs containing the investigational drug(s)

If a subject discontinues before Randomization, the IRT should be notified within five days and the reason for not being randomized should be recorded on the appropriate Case Report Forms.

Randomization will be stratified by body weight assessed at baseline. Stratification ensures a balanced allocation of subjects to treatment groups within the two weight strata: “body weight < 90 kg” or “body weight \geq 90 kg”.

The randomization scheme for subjects will be reviewed and approved by a member of the Randomization Office.

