2.7 Analysis of secondary efficacy objective(s)

2.7.1 Secondary endpoints

PASI 50, PASI 75, PASI 90, PASI 100, and IGA mod 2011 0 or 1 response over time

Summary statistics for PASI 50, PASI 75, PASI 90, PASI 100, and IGA mod 2011 0 or 1 response by visit will be presented in contingency tables and will include absolute and relative frequencies. Confidence intervals for response rates will be derived as well based on the exact method.

For PASI 50, PASI 75, PASI 90, PASI 100, and IGA mod 2011 0 or 1 response at each visit, up to Week 12, comparisons between 2mL AI vs placebo and 2mL AI vs 1mL PFS x 2 will be conducted using logistic regression model with treatment group, body weight stratum and baseline PASI as effects.

For PASI 50, PASI 75, PASI 90, PASI 100, and IGA mod 2011 0 or 1 response, the placebo adjusted response rates (i.e., risk difference) including 95% confidence interval (based on normal approximation) will be derived by visit, up to Week 12. In addition, Fisher's exact test will be applied to the treatment group comparisons between 2mL AI versus placebo. In addition, the risk difference between 2ml AI group vs. 1ml PFS group, including 95% confidence interval (based on normal approximation) may be derived by visit, up to Week 52.

Figures will be provided as well displaying estimates for response rates over time by treatment including 95% confidence intervals.

PASI score over time

Summary statistics will be provided for absolute PASI scores as well as for percent change from baseline by visit and treatment group. Figure will be provided for percentage changes in PASI scores over time.

IGA mod 2011 score over time

Summary statistics for the IGA mod 2011 score over time will be presented by visit and by treatment group in contingency tables. Figures will also be provided.

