2.15 Interim analysis

Week 16 primary analysis will be performed after all subjects have completed Week 16 visit. Additional analyses may be performed to support health authority interactions as necessary. At the End of Study, a final analysis of all data collected up to last study visit (Week 52) will be performed when all subjects have completed the last study visit.

Trial modifications are not planned based on any interim analysis.

3 Sample size calculation

A response rate of 8% for PASI 75 response and IGA mod 2011 0 or 1 response in the placebo group is expected, whereas a response rate of 62% for PASI 75 response and 55% for IGA mod 2011 0 or 1 is the anticipated response in the secukinumab 300 mg 2 mL auto-injector s.c. group.

Placebo-response rates between 3% and 7% have been reported in [Papp et al 2005](#), [Menter et al 2008](#), [Leonardi et al 2008](#), and [Papp et al 2008](#).

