3.1.1 Secondary endpoints

The study should be sufficiently powered (above 90%) to show a response rate of 46% for PASI 90 response if the placebo rate is assumed as 8%.

4 Change to protocol specified analyses

The following analyses have been removed:

- The maximum change (maximum decrease and maximum increase) from baseline within treatment period for each laboratory parameter
- The stratified Van-Eltern testing and Hodges-Lehmann estimates for the absolute value and the percentage change from baseline of DLQI total score.

5 Appendix

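### The PASI/IGA risk differences, and the multiple-imputation fallback test when an arm is at 0% or 100%, leave out the weight stratum used for randomisation; the effect is small and falls mainly on the AI-versus-PFS interval

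*SAP*

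**What the plan says.** **Design and main models.** Protocol 6.3.2 gives the purpose of stratifying: "Stratification ensures a balanced allocation of subjects to treatment groups within the two weight strata". SAP 2.5.2, 2.6.2 and 2.7.1 fit logistic regression with treatment, weight stratum and baseline PASI. Weight category is also the only planned subgroup (SAP 2.2.1).

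**Risk differences.** SAP 5.4.4 obtains them per imputed data set from "TABLES <treatment group>*<response variable>/riskdiff alpha=0.05", which has no stratum term, and pools them. SAP 2.7.1 gives by-visit differences with normal-approximation intervals: AI versus placebo to Week 12 and, optionally, AI versus PFS to Week 52. It adds that Fisher's "exact test will be applied to the treatment group comparisons between 2mL AI versus placebo". SAP 5.4.2 repeats the by-visit differences. Neither section mentions weight.

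**Fallbacks for the co-primaries.** With 0% or 100% responders in an arm, SAP 2.5.2 uses a t-test on the risk difference under multiple imputation and Fisher's test under non-responder imputation. For non-convergence, SAP 2.5.2 and 5.4.3 run exact logistic regression first, then remove covariates with the weight stratum last, and reach Fisher's test only at the end. SAP 5.4.4 instead goes directly to the risk difference.

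**The concern.** When randomisation is stratified on a factor that predicts the outcome, the arms are balanced on it, so a difference in proportions varies less from trial to trial than the crude binomial formula assumes. A crude standard error then overstates the uncertainty. Here the adjusted model and the crude risk difference would be reported side by side for the same endpoints, and when an arm has no responders the crude difference also supplies the test.

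The contrast most exposed is AI versus PFS. Protocol 4.3 makes the PFS arm the reference for efficacy comparisons. SAP 2.7.1 limits the logistic comparison of the two devices to Week 12, so under that section the crude risk difference is the only AI-PFS contrast after Week 12.

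**Working it through.** **1. The plan's own figure.** SAP section 3 states: "the type-I-error will be 2.5% one-sided for comparison"; "With 40 subjects per group and assuming a response rate of 8% for PASI 75 response"; "a response rate of 62% for PASI 75 response and 55% for IGA mod 2011 0 or 1 is the anticipated response"; power "is above 99% for PASI 75 response and IGA mod 2011 0 or 1 response". Exact enumeration of the one-sided Fisher test with 40 per group gives 99.97% for 62% v 8% and 99.72% for 55% v 8%. For PASI 90 (46% v 8%) it gives 97.3%, against the stated figure of above 90%. All three are reproduced.

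**2. Assumptions.** The documents give no response rates by weight. I assume equal strata (20 per stratum and arm) and let d be the difference in response between strata.

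**3. AI versus PFS.** Assume 60% in both arms.
- Crude variance = 2 × 0.60 × 0.40 / 40 = 0.0120; SE 0.1095.
- Stratified variance = 2 × (0.24 − 0.25 d²) / 40.

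| d | Stratified SE | Crude interval wider by | 95% width, crude v stratified (points) |
|---|---|---|---|
| 0 | 0.1095 | 0% | 42.9 v 42.9 |
| 10 points (65%/55%) | 0.1090 | 0.5% | 42.9 v 42.7 |
| 20 points (70%/50%) | 0.1072 | 2.2% | 42.9 v 42.0 |
| 30 points (75%/45%) | 0.1043 | 5.0% | 42.9 v 40.9 |

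Simulation at d = 30 points (200,000 trials): mean crude SE 0.1083 with coverage 95.8%; Mantel-Haenszel with Sato variance 0.1029 with coverage 94.3%.

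**4. AI versus placebo.** With equal strata, the Sato variance reduces algebraically to

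crude variance − 0.5 × d1 × d0 / 40,

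where d1 and d0 are the weight effects in the active and placebo arms. If the placebo rate does not vary with weight, d0 = 0 and nothing is gained, whatever d1 is. Simulation agrees:
- 72%/52% v a flat 8%: 0.0866 crude, 0.0866 Sato.
- 72%/52% v 0%: 0.0758 crude, 0.0758 Sato.

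If the placebo rate did vary, say d1 = 30 and d0 = 7.5 points at 62% v 8%, the variance numerator falls from 0.3092 to 0.3092 − 0.5 × 0.30 × 0.075 = 0.2980, and the crude interval is 1.9% wider.

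A plug-in stratified variance shows a larger apparent gain (crude wider by 1.8% at 20 points and 4.1% at 30 points, taking d0 = d1/4), but its coverage is about 93.4–93.8%, against 93.8–94.7% crude.

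**5. How often the 0% fallback applies.** P(0 of 40 on placebo) = (1 − p)^40: 3.6% at the planned 8%, and 5.5% and 29.6% at the ends of the cited 7% to 3% range.

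**6. Can the choice change a decision?** With 0 of 40 on placebo, the crude Wald test passes from 4 of 40 AI responders: 0.10 / √(0.10 × 0.90 / 40) = 2.11. Fisher's test passes from 6 of 40 (p = 0.013). The chance of 5 or fewer AI responders is about 1 × 10⁻¹⁰ at 62%, 3 × 10⁻⁸ at 55% and 7 × 10⁻⁶ at 46%.

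**The case against.** The strongest reply is that the stratum is already used where inference is made. The primary, key secondary and by-visit logistic models include it, weight subgroups are tabulated, and SAP 2.1 reserves the 95% intervals for estimation. A crude difference is a valid estimate of the marginal effect, and the AI-PFS difference is optional with no hypothesis attached. Protocol 12.6.1 and SAP 5.4.3 also speak of logistic regression at every visit, so the limit to Week 12 is particular to SAP 2.7.1. This stands, and it keeps the point minor. It does not remove it, because SAP 2.5.2 takes a p-value from the crude difference in the 0%/100% case.

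Three stronger readings are tempting, and the documents do not support them.
- *That stratification is lost whenever logistic regression fails.* SAP 2.5.2 and 5.4.3 keep the weight stratum through exact logistic regression and drop it last. Only SAP 5.4.4 goes straight to the crude table.
- *That the crude method endangers the co-primary result or costs power.* Steps 4 and 6 show otherwise.
- *That stratifying is free.* Coverage falls somewhat, and it does not repair the real weakness of the 0% case: an empty placebo arm contributes zero estimated variance, crude or stratified.

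**Conclusion.** The point holds as a minor inconsistency between the design and one family of estimates. The PASI/IGA risk differences and the multiple-imputation test for a 0% or 100% arm omit the randomisation stratum that the main models include.

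The cost is confined mainly to AI versus PFS: an interval about 0.5% too wide at a 10-point weight effect and about 5% at 30 points, equivalent at 30 points to about 10% more subjects (1.0504² = 1.103). It is nil if weight does not predict response. These figures rest on assumed equal strata and an assumed 60% average response in both arms. Against a flat or near-zero placebo rate the Mantel-Haenszel standard error is about equal to the crude one. The stated power figures and the co-primary conclusions are unaffected.

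**What to change.** - In SAP 2.5.2, 2.7.1, 5.4.2 and 5.4.4, define the by-visit and fallback risk differences as stratified by weight category: Mantel-Haenszel weights, a named variance estimator such as Sato's, computed in each imputed data set and pooled by Rubin's rules. Keep the crude difference as descriptive.
- Update the code that follows the table in SAP 5.4.4, because it reads the estimate and standard error from the two-way output. Adding a stratum to the table statement alone is not enough. Putting weight in the BY statement would give separate subgroup results, not a pooled estimate.
- In the same edit, state one sequence for non-convergence, so that SAP 2.5.2 and 5.4.3 agree with 5.4.4.
- State how the variance is handled when an arm has no responders, since stratifying does not settle that.

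The cost is a few lines of code and text, and coverage slightly below that of the crude interval: about 94.3% against 95.8% for AI versus PFS in the 30-point scenario. No change to sample size, data collection or trial conduct is needed.
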